5.1.4 Safety Follow-up Period

Following completion of the 6-week double-blind Treatment Period, all patients will enter the 5-week single-blind Safety Follow-up Period and take 1 tablet of single-blind study drug each morning during this period.

During the 5-week single-blind Safety Follow-up Period, patients are allowed use of rescue medication (acetaminophen) if needed.

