5.1.5 Optional Substudies

During the Screening Visit, patients may choose to participate in 1 or both of the 2 optional substudies.

The first substudy will include approximately 30 patients for intensive blood sampling for determination of LX9211 plasma concentrations to allow for PK parameter estimation, and additional samples for possible biomarker analyses. The PK intensive sampling will occur on Days 1 and 2 and at the Week 6 clinic visit. These patients will be confined to a clinical research unit (CRU) twice during the study for intensive PK evaluation and biomarker evaluation: prior to

and following the first dose of study drug and prior to and following their final dose of study drug (planned for Week 6).

The second optional substudy, a qualitative patient interview, will include approximately 60 patients. The telephone interview will be designed to gain insight and understanding of patients' experiences with symptoms of DPNP and to assess relevance and clinical meaningfulness of symptom improvements (eg, reduction in pain) with LX9211 treatment.

6. Study Population

Up to 282 patients (94/treatment group) are expected to enroll in this study in order to complete 225 (75/treatment group). The sample size may be increased to a maximum of 351 patients based on a planned interim analysis that allows for conduct of a sample size reestimation procedure.

A subset of approximately 30 patients will be recruited to participate in the PK and biomarker analyses optional substudy.

A second substudy will enroll a minimum of 60 patients and not to exceed 85 patients to participate in a qualitative patient interview.

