8.1.5 Qualitative Patient Interview

A telephone qualitative patient interview substudy will be conducted for approximately 60 patients within 2 weeks following the Week 6 Visit or following premature withdrawal.

The purpose of the phone interview will be to gain insight and understanding of patients' experiences with symptoms of DPNP and to assess relevance and clinical meaningfulness of symptom improvements. (eg, reduction in pain).

The qualitative patient interview will be performed as specified in Appendix A.

9. Safety Reporting

It is the responsibility of the Investigator to document all AEs and special situations that occur during the study.

Adverse events will be collected at all study visits as outlined in the Schedule of Study Assessments. Each AE should be recorded using the medical diagnosis; if a diagnosis is not established at the time of the reporting, a symptom or sign in standard medical terminology should be used.

Adverse events should not be solicited with leading questions that suggest specific signs or symptoms. Rather, AEs should be solicited by asking the patient a non-leading question such as: "Do you feel different in any way since receiving the dose or since the last assessment?"

Adverse events that occur after the signing of the informed consent and before the first dose of study drug should be recorded as medical history unless the event is a serious adverse event (SAE) that could be associated with the trial procedures and, which could modify the conduct of the trial, or otherwise specified.

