The second optional substudy is a qualitative patient interview, which will include 60 to 85 patients. The interview will be conducted over the telephone and is designed to gain insight and understanding of patients' experiences with symptoms

[figure not shown]
Statistical Analysis Plan Final v3.0

Lexicon Pharmaceuticals, Inc.
Protocol ID: LX9211.1.201-DPN

Labcorp Study ID: 000000198624

of DPNP and to assess the relevance and clinical meaningfulness of symptom improvements (eg, reduction in pain) with LX9211 treatment.

The study design is presented in the diagram below:

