1 STUDY BACKGROUND AND DESIGN

Lexicon Pharmaceuticals, Inc. (Lexicon) is conducting a phase 2 clinical trial¹ to evaluate the efficacy of LX9211, an oral product for the treatment of diabetic peripheral neuropathic pain (DPNP). As part of the clinical trial, RTI-HS, in collaboration with Lexicon, plans to conduct qualitative interviews with a subset of patients from the study that will supplement the patient-reported data gathered in the clinical trial and help to further understand and describe patients' experiences with DPNP and LX9211.

Data collected during in-depth qualitative interviews will provide a deeper understanding of patients' perceptions of and experiences with DPNP and LX9211 and the relevance and clinical meaningfulness of symptom improvements (e.g., reduction in pain) to patients. The semistructured telephone interviews will be conducted with a subset of English-speaking clinical trial participants (up to 60 patients) who complete or terminate early from the 6-week double-blind treatment phase of the trial.

The overall objective of the qualitative interviews is to gain a more comprehensive understanding of patient experiences with DPNP and LX9211 treatment by collecting information that may not be captured adequately via traditional clinical outcomes assessments. Specifically, the objectives of the qualitative interviews are to obtain a better understanding of the perspectives of patients with DPNP on the following:

- Disease-related burden
- Impact of the disease on patients' lives before starting the clinical trial
- Satisfaction with DPNP treatments used prior to the clinical trial
- Most important to treat and most bothersome aspects of DPNP
- Expectations of study drug
- General experiences with study drug
- Benefits and impact of those benefits
- Importance of improvements experienced during the clinical trial (if experienced)
- Impact of the study drug on daily life/functioning

¹ A Phase 2, Randomized, Double-blind, Placebo-controlled, Parallel-group, Multicenter Study to Evaluate the Efficacy, Safety, and Pharmacokinetics of LX9211 in the Treatment of Diabetic Peripheral Neuropathic Pain (Protocol Number LX9211.201)

- How well the study drug addresses most important/bothersome symptoms
- Satisfaction with and reason(s) for satisfaction or dissatisfaction (if applicable) with the study drug

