 2 = Moderately difficult
 3 = Quite difficult
 4 = Very difficult

- Tell me why you selected that answer.

III. Prestudy Impact/Burden Of DPNP	~ 10 min
--	-----------------

10. **Before starting the study, what impact did diabetic neuropathic pain have on your life, if at all? [Allow for spontaneous reports of impacts. Specific probes are listed below]**

11. **How, if at all, did this pain affect your life before the study? [Probe for impact areas if not spontaneously reported]...**

- a) Daily activities? What kinds of daily activities were impacted?
 - Are there things you could not do because of the pain that you wanted to do?
- b) Mobility (e.g., walking; using stairs; getting up/down from chair or toilet)
- c) Mood/emotions (e.g., depressed mood, anxiety, irritability, anger)
- d) Self-care (e.g., bathing or dressing self; using utensils)
- e) Sleep

12. **What was it about your neuropathic pain or its treatment that bothered you the most before starting the study? [Probe to understand if most bothersome issues are issues related to the pain and/or are treatment-related]**

Why does [repeat most bothersome issue] bother you?

IV. Prestudy Treatment Expectations

~ 5 min

13. Thinking back to before you started the clinical trial, what were some of the reasons you decided to participate in the trial?
 - a) Were some reasons more important to you than others? **[If yes]** Which ones?
14. Before starting the clinical trial, were there specific symptoms/problems that you most wanted the study drug to help? Which ones? Why?
15. How important to you would it be for a neuropathic pain treatment to improve? **[Use the 1-to-5 rating scale below for each symptom the patient reports – examples listed below. Repeat scale as often as needed]**
 - 1 = Not at all important
 - 2 = A little important
 - 3 = Somewhat important
 - 4 = Very important
 - 5 = Extremely important
 - a) Pain
 - b) Numbness
 - c) Tingling/pins and needles
 - d) Weakness

V. During Study Experiences

~ 15 min

Now I would like to talk to you about your experiences during the clinical study. So, thinking about your experiences while you were taking the study drug....

- 16. What were your overall impressions of the study drug?**

- 17. What improvements, if any, did you notice while taking the study drug?**

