[Ask the participant to describe each improvement reported. Allow for spontaneous reports of improvements in symptoms/pain. If not already mentioned, probe to see if the symptoms experienced before the study improved, if so, have the participant describe the improvement and rate the importance of the improvement below]

- 18. Please rate the importance of the improvement in [SYMPTOM from Q4] on the following scale (from 1 to 5). I will read the scale to you:**

 1 = Not at all important
 2 = A little important
 3 = Moderately important
 4 = Very important
 5 = Extremely important

Why?

[If improvements noticed] How soon after receiving the study drug did you notice these improvements?

- a) What, specifically, did you notice first?

VI. Impact of Improvements [If no improvements, skip to Q 23] ~ 10 min

19. Thinking about the improvements [Refer back to improvements listed above] you noticed as a result of the study drug, which are the most important to you? Why?
20. Thinking about the improvements you have seen from the study drug; how did these improvements affect you in your daily life? [Allow for spontaneous responses]

[If not reported spontaneously] How, if at all, did these improvements affect your...

- a) Daily activities? What kinds of daily activities were impacted?
 - Are there things you can now do or do better because of improvements in neuropathic pain?
- b) Mobility (e.g., walking; using stairs; getting up/down from chair or toilet)
- c) Mood/emotions (e.g., depressed mood, anxiety)
- d) Self-care (e.g., bathing or dressing self; using utensils)
- e) Sleep

21. You mentioned that that [insert response from Q14] bothered you the most. How, if at all, did the study drug improve these issues?

VII. Treatment Satisfaction and Preference

~ 5 min

22. Overall, how satisfied are you with the study drug as a treatment for diabetic neuropathic pain?

- 0 = Not at all satisfied
- 1 = A little satisfied
- 2 = Moderately satisfied
- 3 = Quite satisfied
- 4 = Very satisfied

- a) Tell me why you selected that response. [Probe to better understand what specifically influenced participant's response to this question]

23. Thinking about the study drug compared to the neuropathic pain treatment(s) you had tried before the study, which did you prefer:

- Study drug
- A previous medication

Why?

24. Would you have continued taking the study drug if you could have?

- Yes
- No

Why?

VIII. Summing Up

~ 2 min

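### The exit interview of Week 6 completers falls inside the single-blind placebo follow-up, and its wording implies that study drug has ended

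*SAP*

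**What the plan says.** Protocol Section 5.1.4 says that after Week 6 "all patients will enter the 5-week single-blind Safety Follow-up Period and take 1 tablet of single-blind study drug each morning during this period". The Schedule of Events and SAP Section 7.2 show that the follow-up tablets are placebo. Daily rating of BPI-DPN Question 5 continues to the end of follow-up (Protocol Section 8.1.4).

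The interview substudy is held "within 2 weeks following the Week 6 Visit or following premature withdrawal" (Protocol Section 8.1.5; the schedule footnote agrees for Week 6). The legend to Figure 5.1-1 gives 2 to 3 weeks instead. Protocol Section 6 sets the size at "a minimum of 60 patients and not to exceed 85 patients", and SAP Section 2.2 gives the same range. The qualitative analysis plan filed with the SAP, dated 02 April 2020, allows at most 60 and includes patients who stopped early.

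The interview guide (Appendix A of that plan) introduces its section on in-study experience with "thinking about your experiences while you were taking the study drug". Its last treatment question, Q24, is "Would you have continued taking the study drug if you could have". The guide gives no instruction on protecting the single blind.

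Two planned analyses draw on the follow-up:

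- Time to loss of efficacy (SAP Section 7.6.2.6) covers patients with at least a 30% reduction at Week 6. Its event is leaving the follow-up for lack of efficacy.
- The cumulative distribution of percent change in ADPS from Week 6 to Week 11 (SAP Section 7.6.5.6).

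**The concern.** A single-blind follow-up serves its purpose only if patients cannot tell which period they are in. The Amendment 1 summary shows that this was intended: visit names were added to help keep the blind, and labels carry no study period. A completer who took a tablet that morning, and is then asked about study drug as something past that could not be continued, may conclude that the current tablet is something else.

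That belief can raise self-rated pain or prompt a decision to leave. Both follow-up analyses rest on exactly those two things, and time to loss of efficacy is the more exposed because its event is a decision to stop. The qualitative plan predates Amendment 2, which fixed time to loss of efficacy to Weeks 6 to 11 and added the Week 6 to Week 11 distribution. SAP Section 7.6.3 plans no sensitivity analysis for secondary or other endpoints, so nothing at present would show whether the interview mattered.

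**Working it through.** **Denominator.** Protocol Section 10.1 assumes a difference of 1, SD 2 and 75 completers per group.

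- Standard error: 2 × √(2/75) = 0.327, so the standardized difference is 1/0.327 = 3.062.
- The two-sided Dunnett critical value for two comparisons (correlation 0.5) is 2.212. Power = Φ(3.062 − 2.212) = Φ(0.850) = 80.2%, against the stated 80%.
- Dropout: 75/(1 − 0.20) = 93.75, rounded up to 94 per group; 3 × 94 = 282.

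The plan's figures reproduce. The maximum after sample size re-estimation is 351.

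**Share of patients interviewed** (interviews ÷ total enrolled)

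| Interviews | N = 282 | N = 351 |
|---|---|---|
| 60 | 60/282 = 21.3% | 60/351 = 17.1% |
| 85 | 85/282 = 30.1% | 85/351 = 24.2% |

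These are ceilings on the number exposed, because early withdrawals count among the interviews. Relative to the 225 planned completers (3 × 75), and only if no early withdrawal were interviewed, the shares would be 60/225 = 26.7% and 85/225 = 37.8%. The share among Week 6 responders, the set used for time to loss of efficacy, cannot be derived from the documents.

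**Overlap with the diary**

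- Follow-up lasts 5 × 7 = 35 days.
- Interview by day 14 of follow-up: at least 35 − 14 = 21 diary days come after it.
- Interview by day 21 (Figure 5.1-1 legend): at least 35 − 21 = 14 diary days come after it.
- The Week 6 visit is targeted at Day 43 (SAP Table 1.2) with a ±3-day window. The latest interview is then Day 43 + 3 + 21 = Day 67. The Week 11 ADPS uses Days 71 to 77 (SAP Table 1.1), so for a completer seen within these windows the Week 11 value always follows the interview.

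**What the wording can disclose.** It can suggest that the treatment period is over. Nothing in the guide indicates whether the patient received LX9211 or placebo. The first interview analysis uses blinded data, and the sponsor supplies treatment assignment afterwards (qualitative plan, Sections 2 and 4.4).

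**The case against.** The strongest case against has four parts.

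1. **What patients knew is not visible here.** The consent text and the interviewers' procedure guide are not among the documents. Q24 is hypothetical: it implies that drug has ended but does not say so.
2. **The guide serves two groups.** For early terminators the past tense is literally correct. Some other items use the present tense.
3. **The exposed analyses carry little weight.** Secondary endpoints are exploratory (SAP Section 7.6). Time to loss of efficacy has Kaplan-Meier estimates with no between-arm test specified, and the Week 6 to Week 11 distribution is a descriptive plot.
4. **The script is the same in every arm**, so no between-arm bias has been shown.

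The first three stand and limit the point to a modest one. The fourth stands in part. Patients reporting no improvement skip the section on improvements attributed to study drug, so improvers hear more of this framing, and only Week 6 responders enter the time-to-loss analysis. If LX9211 works, these patients would be found more often in the active arms. That is a possible route to an unequal effect, not evidence of one.

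A reader might infer from the 30% figure that up to 30% of the trial is unblinded. The documents do not support that. The randomized arm is not disclosed, the primary endpoint is measured before a completer is interviewed, and 30% needs the maximum number of interviews, the unincreased sample size and no early withdrawals among those interviewed.

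**Conclusion.** The point holds in a limited form. For Week 6 completers the interview lies inside the single-blind placebo follow-up, and its wording implies that study drug has ended, with at least 14 to 21 diary days still to come. The single blind of that period may be weakened in at most 17% to 30% of patients. The randomized allocation and the primary result are not affected. What is exposed is the reading of time to loss of efficacy and of the Week 6 to Week 11 pain distribution as blinded withdrawal of drug.

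This rests on two assumptions: that the consent form did not already tell patients that the follow-up tablets are placebo, and that interviewers follow the guide as printed. The size of any expectation effect cannot be estimated from the documents. I would label this a cheap improvement.

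**What to change.** **Guide.** For completers, anchor the in-study and satisfaction questions to the interval between the Day 1 (randomization) visit and the Week 6 visit, without suggesting that the tablets changed. Q24 could read: *If the tablets you took between those two visits were available to you, would you want to take them?* The anchor must be the randomization visit, because the first dose taken in clinic is run-in placebo. The question must not ask about the tablets now being taken, which are placebo. Keep the present wording for early terminators.

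**Analysis.** The guide already has the interview date read onto each recording. Use those dates for one sensitivity summary that censors time to loss of efficacy at the interview date and shows the Week 6 to Week 11 distribution without interviewed completers. Dropping post-interview diary days alone would not do this. It removes no loss-of-efficacy events, because the event is termination rather than a diary score, and it deletes the Week 11 value of every interviewed completer.

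**Text.** Reconcile the interview window in the Figure 5.1-1 legend with Protocol Section 8.1.5 and the schedule footnote. The number of interviews also needs one value: Protocol Section 6 and SAP Section 2.2 differ from Protocol Sections 5.1.5 and 8.1.5 and from the qualitative plan.

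**Cost.** A revised guide with ethics notification, and one extra summary. Wording will differ slightly from interviews already done. The sensitivity summary has fewer patients, and because the substudy is optional, those left are self-selected. Anchored wording reduces the hint but may not remove it entirely. If all interviews are complete, the sensitivity summary is still worth adding.

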Appendix B. ATLAS Codebook (Draft 1; 17 February 2020)

PARTICIPANT INTERVIEWS: LX9211 DRAFT CODEBOOK: GENERAL CODING POINTS

- Operational definitions are for coder reliability, not necessarily analytic interpretation
- Codes and their operational definitions evolve based on the transcript text reviewed. These codes and their definitions are subject to change throughout the coding process.

Code	Operational Definition
1.0 Treatment Assignment	Treatment assignment data provided by Lexicon
1.1 Treatment_10mg	Patient was on study drug (10 mg)
1.2 Treatment_20mg	Patient was on study drug (20 mg)
1.3 Placebo	Patient was on placebo
2.0 Background	Code response to background questions
2.1 Age at diabetes diagnosis	Response to the question "About how old were you when you diagnosed with diabetes?"
2.3 Time since DPNP symptoms began	Response to the question "About how long ago did you start to experience neuropathic pain associated with your diabetes?"
3.0 DPNP Symptoms Before Study	Code all information about the symptoms participant experienced before the clinical trial
3.1 Symptom_Numbness	Neuropathic pain described as numbness or dead feeling
3.2 Symptom_Tingling	Neuropathic pain described as tingling or pins and needles
3.3 Symptom_Weakness	Neuropathic pain described as weakness
3.4 Symptom_Sensitivity	Neuropathic pain described as very sensitive or sensitivity to touch and pressure
3.5 Symptom_Other descriptions of pain	Any other descriptions of neuropathic pain
3.6 Location_Hands	Neuropathic pain in the hands
3.7 Location_Arms	Neuropathic pain in the arms
3.8 Location_Feet	Neuropathic pain in the feet
3.9 Location_Legs	Neuropathic pain in the legs
3.10 Location_Other	Neuropathic pain in any other location
3.11 Location_Severe	Response to the question "Were there specific locations where the pain was more severe than others before starting the clinical trial? Which ones?"
3.12 Symptom_Bothersome	Response to the question "Were specific symptoms more bothersome to you than others before the clinical trial? Which ones?"

Code	Operational Definition
4.0 Pre-trial Satisfaction	Code responses to satisfaction and management questions. Code both quantitative response and reasons why.
4.1 Pre-trial treatment satisfaction	Responses to the questions "Before starting the clinical trial, overall, how satisfied were you with your neuropathic pain treatment?" and "Tell me why you selected that answer."
4.2 Pre-trial pain management	Responses to the questions "Before starting the clinical trial, how easy or hard was it for you to manage your neuropathic pain?" and "Tell me why you selected that answer."
5.0 DPNP Impacts Before Clinical Trial	Code response to the question "Before starting the study, what impact did diabetic neuropathic pain have your life, if at all" and follow-up probes.
5.1 Impact_daily_activities_work	Impact on any gainful activities (e.g., absenteeism, productivity)
5.2 Impact_daily_activities_home	Impact on activities completed at home (running a household, caring for family)
5.3 Impact_mobility	Impact on walking, using stairs, getting up/down from a chair or toilet, etc.
5.4 Impact_mood/emotions	Impact on mood/emotions/feelings, such as depressed mood, anxiety, irritability, anger
5.5 Impact_self-care	Impact on ability to engage in self-care activities such as bathing, dressing, using utensils
5.6 Impact_sleep	Impact on ability to get to sleep or stay asleep
5.7 No_impact	Patient reports no impacts
5.8 Most bothersome problem - DPNP_Symptom	Response to the question "What was it about your neuropathic pain or treatment that bothered you the most before starting the study?" for all symptom responses and related probes
5.8 Most bothersome problem - DPNP_Treatment	Response to the question "What was it about your neuropathic pain or treatment that bothered you the most before starting the study?" for all treatment responses and related probes

Code		Operational Definition
6.0 Clinical Trial Desires/Expectations		Code responses to questions related to prestudy treatment expectations
6.1	Reasons_CT	Response to question "Thinking back to before you started the clinical trial, what were some of the reasons you decided to participate in the trial?" and "Were some reasons more important to you than others? Which ones?"
6.2	Sx_Treat_CT	Response to question "Before starting the clinical trial, were there specific symptoms that you most wanted the study drug to help? Which ones? Why?"
6.3	Sx_Treat_Importance_Numbness	Response to question "How important would it be to you for a neuropathic pain treatment to improve numbness?"
6.4	Sx_Treat_Importance_Tingling	Response to question "How important would it be to you for a neuropathic pain treatment to improve tingling?"
6.5	Sx_Treat_Importance_Weakness	Response to question "How important would it be to you for a neuropathic pain treatment to improve weakness?"
6.6	Sx_Treat_Importance_Sensitivity	Response to question "How important would it be to you for a neuropathic pain treatment to improve sensitivity?"
6.7	Sx_Treat_Importance_Other	Response to question "How important would it be to you for a neuropathic pain treatment to improve [any other symptom patient reported]?"
7.0 Study Experiences		Code any symptom improvement mentioned (no matter how slight) and description of improvement.
7.1	Overall impressions of the study drug	Code response to question "What were your overall impressions of the study drug?"
7.2	Improve_Numbness	Neuropathic pain described as numbness or dead feeling
7.3	Improve_Tingling	Neuropathic pain described as tingling or pins and needles
7.4	Improve_Weakness	Neuropathic pain described as weakness
7.5	Improve_Sensitivity	Neuropathic pain described as very sensitive or sensitivity to touch and pressure
7.6	Improve_Other	Any other descriptions of neuropathic pain
7.12	No_Improvement	If the study participants reported no improvements in symptoms during the clinical trial
7.13	Noticed improvements	Code response to question "How soon after receiving the study drug did you notice these improvements" and all related probes

Code		Operational Definition
8.0 Importance of Symptom Improvement		These codes are participant's responses to importance rating of each symptom improvement from interview guide. Code entire response.
8.1	Why_Important	Code entire importance rating, why
8.2	Most Important Improvement	Response to the following question: "Thinking about the improvements you noticed as a result of study drug, which are the most important? Why?"
9.0 Impact of Improvement		Code any reports of improvements/reductions in the impact of their DPNP due to improvements in symptoms during study treatment
9.1	Tx_Impact_daily activities_work	Impact on any gainful activities (e.g., absenteeism, productivity)
9.2	Tx_Impact_daily activities_home	Impact on activities completed at home (running a household, caring for family)
9.3	Tx_Impact_mobility	Impact on walking, using stairs, getting up/down from a chair or toilet, etc.
9.4	Tx_Impact_mood/emotions	Impact on mood/emotions/feelings, such as depressed mood, anxiety, irritability, anger
9.5	Tx_Impact_self-care	Impact on ability to engage in self-care activities such as bathing, dressing, using utensils
9.6	Tx_Impact_sleep	Impact on ability to get to sleep or stay asleep
9.7	Tx_Impact_most bothersome	Treatment improvement (if any) on symptom or impact reported as most bothersome
